The Effects of VR Interactive Games on Balance and Quality of Life Enhancement for Elderly in the Community

> Unique Protocol ID: N202210004 Document Date: June 26, 2023

Abstract

Thesis title: Examining the effectiveness of a virtual reality interactive game on physical fitness and quality of life in community-dwelling elderly people

Name of degree and program: Master's program in Long-term Care, Taipei Medical University

Graduate student: [name]

Thesis directed by: [name], Associate [name] Ph.D. Program in Gerontology and Long-term Care, Taipei Medical University

Background: Currently, community exercise courses are mostly guided by nurses and there are few opportunities for participating elderly people to interact with others during exercise. An interactive game was developed to allow elderly people participating in community activities to use game feedback to increase enjoyment and competitiveness in team games. Besides improving physical fitness, and increasing motivation and willingness to continue participating in exercise, this can also improve the quality of life.

Objective: To examine whether a virtual reality interactive game exercise can help improve the physical fitness and quality of life of elderly people. Methods: Elderly people aged 65 years and above who participate in community activities were recruited and randomized into the experimental group and control group. The experimental group completed 36 episodes of exercise intervention using the interactive game,

I

spread over 12 weeks, while the original routine exercise was used as the course content in the control group. Both groups underwent 36 episodes of intervention of one hour each time, thrice a week for 12 consecutive weeks. Assessments of functional physical fitness and satisfaction with quality of life were performed before and after intervention and the statistical significance was set as p < 0.05.

Results: After 36 weeks of virtual reality interactive game interaction, the post-test scores for 2-minute step test (p<0.001), right chair sit-and-reach test (p=0.010), left chair sit-and-reach test (p=0.002), psychological quality of life (p=0.033), and environmental quality of life (p=0.048) of the experimental group were all significantly higher than those of the control group.

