From the synthesis of the above literature, it is evident that the primary goal of "healthy aging" is to maintain and enhance the physical function of the elderly population, enabling them to lead happy, satisfying, and fulfilling lives. The decline in functional abilities and the increase in sedentary behavior among the elderly are closely related, making it crucial to address how to maintain their physical function, prevent or delay disability, reduce medical and social costs, and improve quality of life. Regular exercise is recognized as the best strategy for improving the sensory-motor system and maintaining balance to prevent falls. By designing group activities that increase the atmosphere of group activities and incorporating game feedback and interactive processes with others, participants can become highly engaged and focused within the social group. They can feel relaxed, relieved of stress, and experience mood changes during facility activities. This increases motivation and willingness to continue participating in exercise and accomplishing tasks during the game, boosting confidence among the elderly and consequently enhancing their quality of life by redefining the value and meaning of life.

Chapter 3: Research Methodology Section 1: Research Design

This study adopts an experimental design with a pre-test and post-test for two groups. Convenience sampling is utilized as the sampling method, and data collection is conducted through questionnaires and measurement evaluation scales. The research investigates the intervention of integrating VR interactive games to assist in improving balance function and lower limb strength among the elderly, thereby enhancing their quality of life. The proposed intervention research framework is depicted below (Figure 2).

[figure not shown]

Figure 2 Research framework diagram of using virtual reality interactive games to improve balance and quality of life of community elders

Section 2: Research Site, Participants, and Ethical Considerations Research Site:

This study will be conducted among community-based activities and voluntary participants aged 65 and above.

Research Participants:

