The sample size for this study is calculated using G-power 3.1.9.7 statistical software to determine the effect size. According to Cohen (1988), effect sizes are categorized as large (0.80), medium (0.50), and small (0.20). Since most research results have an effect size of 0.50, this study sets the criterion of at least a medium effect size. With α =0.05, statistical power (power)=0.80, and effect size set at 0.5, the estimated sample size is 60 individuals. Considering potential changes in the elderly or refusal to participate, a dropout rate of 15% is estimated. Therefore, a total of 70 elderly individuals from community-based activities will be recruited for this study. The inclusion criteria for this study are as follows: (1) aged 65 and above, (2) able to communicate in Mandarin or Taiwanese and willing to complete interviews or self-administered questionnaires, (3) no mobility impairments (e.g., stroke, Parkinson's disease, motor neuron diseases), (4) no severe cardiovascular diseases, (5) no degenerative joint diseases or acute attacks in the past three months, (6) lower limb joint surgery performed more than three months ago, and (7) no dizziness or any unstable health conditions that hinder exercise. During the study period, participants who do not engage in physical

activity for more than three weeks or have missing pre-test or post-test data will be excluded from the statistical analysis.

Ethical Considerations:

Prior to conducting the study, the research proposal will be submitted to the Institutional Review Board (IRB) for review and approval. Approval was obtained from the Taipei Medical University Joint Institutional Review Board (TMU-JIRB) on November 24, 2022, with the approval letter numbered N202210004 (see Appendix 1). This study aims to investigate the effects of VR interactive games as part of exercise prescriptions on the balance function and lower limb strength of elderly participants.

Section 3: Intervention Tools

Hardware Setup:

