This study aims to understand the impact of intervention on the functional fitness and quality of life of elderly participants befor and after the intervention. The assessment tools used include functional fitness tests and a quality of life questionnaire, along with the collection of basic participant information. Both groups underwent pre-tests befor the intervention, which included a fall risk assessment, functional fitness assessment, and quality of life satisfaction survey. After completing the 12-week, 36-session intervention, post-tests were conducted to measure the effectiveness of the intervention.

1. Basic Participant Information:

Includes gender, age, exercise habits, self-perceived health status questionnaire, and Body Mass Index (BMI).

2. Functional Fitness Tests:

(a) Chair Stand Test:

Measures lower body strength/endurance.

Participants sit in a chair without armrests and stand up as many times as possible within 30 seconds.

(b) Chair Sit and Reach Test:

Assesses lower body flexibility.

Participants sit on the edge of a chair with one knee bent at 90 degrees and try to reach their toes with their hands. The distance between the fingertips and toes is measured.

(c) 8-Foot Up-and-Go Test:

Evaluates agility and dynamic balance.

Participants sit in a chair, stand up upon hearing a signal, walk around a designated point 8 feet away, and return to the chair. The time taken to complete the task is recorded.

(d) 2-Minute Walk Test:

Measures aerobic endurance.

Participants walk in place for 2 minutes, and the number of times the knees are lifted to a specific height is counted.

3. Quality of Life Questionnaire:

Administered using the "Taiwanese version of the World Health

Organization Quality of Life Questionnaire-Brief Form

(WHOQOL-BREF Taiwanese version)."

Consists of 28 questions divided into four domains: physical health, psychological health, social relationships, and environment.

Each question is scored on a Likert scale ranging from 1 (very poor) to 5 (very good), with higher scores indicating better quality of life. Demonstrates good reliability with Cronbach's α and split-half reliability of 0.92 and 0.93, respectively. Section 6 Data Processing and Statistical Analysis

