less than 30 minutes	0 (0%)	3 (9.1%)	
more than 30 inutes	22 (73.3%)	15 (45.5%)	
30-60 minutes	8 (26.7%)	15 (45.5%)	
Falls experience in the past			1.034 (0.669)
year			
No falls	23 (76.7%)	25 (75.8%)	
≤3 次	6 (20.0%)	5 (15.2%)	
>3 次	1 (3.3%)	3 (9.1%)	

Table 3 Descriptive Statistics

Section 2: Comparison of Functional Fitness

1. Analysis of Demographic Data

Before the intervention of virtual reality interactive gaming, the participants' functional fitness, including height, weight, lower limb muscle endurance, lower limb flexibility, and agility, were assessed descriptively.

In the pre-test assessment, there were no significant differences between the experimental group and the control group in terms of fitness and quality of life, as indicated by independent samples t-tests, as shown in Table 4.

2. Comparison of Pre-test and Post-test within the Experimental and Control Groups

The results of dependent samples t-tests (Table 5) showed statistically significant improvements in four assessment outcomes in the experimental group, including the 2-minute step test (p < 0.001), left and right chair sit and reach (p < 0.001, p = 0.003), and psychological quality of life (p = 0.008).

In the control group, there was a statistically significant improvement in one assessment outcome, the 30-second chair stand test (p = 0.001).

	Test group (N=30)	Control group	t value (p) or
		(N=33)	Z value (p)
pretest assessment			
BMI	27.0 ± 3.5	25.4 ± 3.8	1.77 (0.077) §
30 seconds sit and stand	16.3±4.6	17.7±5.2	-1.19 (0.234) §
2 minutes to step	96.0±20.7	92.5±25.4	0.60 (0.548)
The seat body bends forward (right)	2.9±10.1	2.6±12.0	0.25 (0.799) §
The seat body bends forward (left)	1.2±11.2	1.4±13.4	-0.08 (0.935)‡
Get up and walk Around at 2.4 meters	8.5±3.2	8.4±3.6	0.70 (0.483) §
Physiological quality of life	10.8±1.4	11.4±1.5	-1.75 (0.086)‡
Psychological quality of life	11.1±1.8	11.7±1.8	-1.28 (0.200) §
Quality of social life	11.2±1.9	11.4±1.1	-0.652 (0.515)§
Environment quality of life	10.6±2.2	10.3±2.0	0.090 (0.928) §

Table 4Functional fitness pre-test of the experimental group and the

control group

[‡] Using independent sample t test

§Using the Mann-Whitney U test

Table 5 Intra-group pre- and post-test comparison between the

experimental group and the control group

		Test g	roup (N=30))		Control	group (N=33	3)
			score				score	

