	protoct	posttast	difference	t value (p)	protost	nasttast	difference	t value (p)
	pretest	posttest	(Pre-test-P	或	pretest	posttest	(Pre-test-P	or
			ost-test)	S value (p)			ost-test)	S value (p)
	Mean ±	standard	deviation	-	Mean ±	standard	deviation	-
BMI	27.0 ± 3.5	26.9±3. 6	0.1±1.0	16.5 (0.741)	25.4 ± 3.8	25.3±3.7	0.1±0.4	75 (0.071)
30 seconds sit and stand	16.3±4.6	17.1±4. 4	-0.9±3.1	-56.5 (0.174)	17.7±5.2	18.5±4.9	-0.8±1.5	-83.5 (0.001)
The seat body bends forward (right)	96.0±20.7	121±25. 7	-26.6±31.2	-4.67(<0.001) §	92.5±25.4	98±20.2	-3.8±15.0	-1.47(0.151) §
The seat body bends forward (left)	2.9±10.1	7.3±9.6	-4.4±7.4	-140 (<0.001)	2.6±12.0	2.9±12.3	-0.3±2.8	0 (1.000)
Get up and walk Around at 2.4 meters	1.2±11.2	5.9±9.6	-4.9±8.1	-3.29 (0.003) §	1.4±13.4	2.9±13.2	-0.2±1.5	-0.79(0.433) §
Physiological quality of life	8.5±3.2	8.3±2.4	0.2±2.9	33 (0.507)	8.4±3.6	8.2±3.4	0.1±0.7	39 (0.384)
Psychological quality of life	10.8±1.4	11.1±1. 4	-0.1±0.4	-1.31 (0.202) §	11.4±1.5	11.3±1.4	0.0±0.1	1.00(0.325) §
Quality of social life	11.1±1.8	11.3±1. 7	-0.2±0.3	-18 (0.008)	11.7±1.8	11.7±1.9	-0.0±0.1	-0.5 (1.000)
Environment quality of life	11.2±1.9	11.3±1. 8	-0.1±0.4	-1.5 (0.500)	11.4±1.1	11.4±1.1	0.0±0.0	_*
The seat body bends forward (right)	10.6±2.2	10.6±2. 2	-0.0±0.1	-1.5 (0.500)	10.3±2.0	10.3±2.0	0.0±0.0	_*

§The Wilcoxon sign test is used, and the rest uses the dependent sample t test.

3. Comparison of Post-test between Experimental and Control Groups

Due to significant differences in demographic data and pre-test assessments between the experimental and control groups, particularly in the education level variable, and considering age as an important control variable, analysis of covariance (ANCOVA) was conducted to compare the post-test scores between the experimental and control groups. Age, education level, and pre-test scores were controlled for in the analysis. Intention-to-treat analysis was used.

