The results of ANCOVA analysis (Table 6) revealed that the post-test scores of the experimental group were significantly higher than those of the control group in five assessment outcomes, including the 2-minute step test (p < 0.001), right chair sit and reach (p = 0.010), left chair sit and reach (p = 0.002), psychological quality of life (p = 0.033), and environmental quality of life (p = 0.048). Additionally, the differences in fitness (except for the 30-second chair stand test) and quality of life had effect sizes (partial eta squared) ranging from 0.011 to 0.267, indicating moderate to substantial intervention effects. These results suggest that the intervention in this study was more effective in improving the aforementioned fitness and quality of life compared to regular community activities.

	StatisticsF /(p)	effect size (partial eta
		squared)
BMI	0.195 (0.661)	0.003
30 seconds sit and stand	0.015 (0.904)	0.000
The seat body bends forward (right)	21.154 (<0.001)	0.267
The seat body bends forward (left)	7.091 (0.010)	0.109
Get up and walk Around at 2.4 meters	10.294 (0.002)	0.151
Physiological quality of life	0.667 (0.418)	0.011
Psychological quality of life	0.956 (0.332)	0.016
Quality of social life	4.766 (0.033)	0.076
Environment quality of life	1.405 (0.241)	0.024
The seat body bends forward (right)	4.080 (0.048)	0.066

Table 6Post-test comparison between the experimental group and the

control group

Note: This analysis uses ANCOVA to control the pretest scores and other significant influencing factors

in the pretest. The control variables include: age, education level, and pretest scores of each variable.

Section 3: Analysis and Comparison of Quality of Life Questionnaire

Upon statistical analysis of pre-test and post-test scores (Table 7), it was found that in the experimental group, there was a difference of 0.4points in the physical domain (p = 0.202), no difference in the psychological domain (p = 0.008), a difference of 0.2 points in the social relationships domain (p = 0.500), and no difference in the environmental domain (p = 0.500). In contrast, in the control group, there was a difference of 0.4 points in the physical domain (p = 0.325), no difference in the psychological domain (p = 1.000), and no difference in the social relationships and environmental domains. The results indicate a significant change in the quality of life in the physical domain for the experimental group.

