Technical Issues:Connectivity issues and delays between the game system and sensors were common. Testers had to ensure that the module vibrated during pairing, leading to delays and frustrations among the

elderly participants, especially when community activity schedules were tight.

To address these issues, a user-friendly model with enhanced motivation and ease of operation should be developed for the elderly. Developing a community-based digital learning support system is a worthwhile future direction. Although age-related decline in physical function is inevitable, weekly VR interactive game exercise training can improve strength, flexibility, and balance in the elderly, enhancing their activity capacity and quality of life.Furthermore, integrating virtual reality interactive games into regular community activity programs led by professionals can foster enthusiasm and motivation among the elderly through peer companionship and encouragement. The innovative and visually engaging feedback exercise in the virtual reality interactive game designed in this study offers a novel direction and mindset for exercise training tailored to community-dwelling seniors.

Chapter 6 Conclusion

The 36-week course activities of virtual reality interactive games can significantly improve the physical fitness, psychological and environmental quality of life of the elderly in the community.

Chinese references

 "Analysis of Elderly Patients Presenting to the Emergency Department Due to Falls." Journal of Geriatric Medicine and Gerontology, 10(1), 16-27. DOI :

10.29461/TGG.201502_10(1).0002

- Executive Yuan, Council for Economic Planning and Development. (2013, February 27). "Population Projection for the Republic of China (Taiwan) from 2012 to 2060." Retrieved from http://www.cepd.gov.tw/m1.aspx?sNo=0000455

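### Tables 5 and 6 are one label off from row 3, so the up-and-go prints a false p = 0.002, and no reported test supports Chapter 5's strength and balance claim

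*Combined protocol and SAP*

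**What the plan says.** Chapter 3 says the study looks at whether VR games "assist in improving balance function and lower limb strength among the elderly" (Section 1) and at effects "on the balance function and lower limb strength of elderly participants" (Section 2, Ethical Considerations). Section 5 assigns lower-body strength to the 30-second chair stand. Of the 8-foot (2.4 m) up-and-go it says: "Evaluates agility and dynamic balance".

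In Chapter 4, Section 2.3, the ANCOVA text lists five significant outcomes: the 2-minute step (p < 0.001), psychological and environmental quality of life (0.033 and 0.048), and "right chair sit and reach (p = 0.010), left chair sit and reach (p = 0.002". The Abstract agrees: "right chair sit-and-reach test (p=0.010), left chair sit-and-reach test (p=0.002". Neither lists the up-and-go or the chair stand. Table 6, introduced by that text, prints F = 10.294, p = 0.002 against the up-and-go.

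For within-group results, Section 2.2 gives "left and right chair sit and reach (p < 0.001, p = 0.003" and calls them dependent-samples t-tests. The Table 5 footnote says of the rows marked §: "The Wilcoxon sign test is used, and the rest uses the dependent sample t test".

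Chapter 5, Section 4 then says "weekly VR interactive game exercise training can improve strength, flexibility, and balance in the elderly".

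**The concern.** Table 6 and the text that introduces it give the same p-value to different outcomes. A reader who uses the table alone finds a significant balance effect that belongs to a flexibility test, on one of the two functions Chapter 3 says are under study. Chapter 5 then claims strength and balance benefits.

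The prose adds to the confusion. Chapter 5, Sections 1 and 2 call the sit-and-reach results chair stands, probably a translation slip, and this reads like evidence on strength. Chapter 4, Section 3 calls the VR arm's physical-domain change significant, although the same paragraph and Table 7 give p = 0.202. Section 2.3 exempts only the chair stand when it describes partial eta squared values from 0.011 upward as moderate to substantial effects, so it counts the up-and-go among them.

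**Working it through.** **1. Which outcome each row holds.** Table 4 carries all ten labels. Table 5's pre-test means match Table 4's, row for row. In Tables 5 and 6 the step label is missing and the right-reach label appears in rows 3 and 10.

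| Row | Label printed in Tables 5 and 6 | Table 5 pre-test, VR / control | Owner of these values in Table 4 |
|---|---|---|---|
| 1 | BMI | 27.0 / 25.4 | BMI |
| 2 | Chair stand | 16.3 / 17.7 | Chair stand |
| 3 | Right reach | 96.0 / 92.5 | 2-minute step |
| 4 | Left reach | 2.9 / 2.6 | Right reach |
| 5 | Up-and-go | 1.2 / 1.4 | Left reach |
| 6 | Physical QoL | 8.5 / 8.4 | Up-and-go |
| 7 | Psychological QoL | 10.8 / 11.4 | Physical QoL |
| 8 | Social QoL | 11.1 / 11.7 | Psychological QoL |
| 9 | Environmental QoL | 11.2 / 11.4 | Social QoL |
| 10 | Right reach (again) | 10.6 / 10.3 | Environmental QoL |

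Table 7 confirms the shift. It gives physical 10.8 to 11.1, p = 0.202, and psychological 11.1 to 11.3, p = 0.008. Table 5 prints these under psychological and social.

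**2. Reproducing Table 6.** With 63 analysed and group, age, education and pre-test in the model, error df = 63 − 5 = 58 (assuming education is a single-df term). Then p = P(F(1,58) > F) and partial eta squared = F/(F + 58).

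| Row | Outcome by row order | F | p printed / recomputed | Partial eta squared printed / recomputed |
|---|---|---|---|---|
| 1 | BMI | 0.195 | 0.661 / 0.660 | 0.003 / 0.003 |
| 2 | Chair stand | 0.015 | 0.904 / 0.903 | 0.000 / 0.000 |
| 3 | 2-minute step | 21.154 | <0.001 / <0.001 | 0.267 / 0.267 |
| 4 | Right reach | 7.091 | 0.010 / 0.010 | 0.109 / 0.109 |
| 5 | Left reach | 10.294 | 0.002 / 0.002 | 0.151 / 0.151 |
| 6 | Up-and-go | 0.667 | 0.418 / 0.417 | 0.011 / 0.011 |
| 7 | Physical QoL | 0.956 | 0.332 / 0.332 | 0.016 / 0.016 |
| 8 | Psychological QoL | 4.766 | 0.033 / 0.033 | 0.076 / 0.076 |
| 9 | Social QoL | 1.405 | 0.241 / 0.241 | 0.024 / 0.024 |
| 10 | Environmental QoL | 4.080 | 0.048 / 0.048 | 0.066 / 0.066 |

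The numbers cohere, and the five significant rows then match the text's five outcomes exactly. Only the labels are wrong.

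**3. Strength and balance.** Up-and-go: p = 0.418 between groups, 0.507 within VR. Chair stand: 0.904 and 0.174. Rough size from the Table 5 changes (Welch, n = 30 and 33, unadjusted; positive favours VR):
- Up-and-go, 0.2 ± 2.9 v 0.1 ± 0.7: difference 0.1 s (seconds assumed); SE = √(2.9²/30 + 0.7²/33) = 0.54; 95% CI −1.0 to 1.2.
- Chair stand, 0.9 ± 3.1 v 0.8 ± 1.5: difference 0.1 stands; SE = √(3.1²/30 + 1.5²/33) = 0.62; 95% CI −1.2 to 1.4.

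**4. Table 5 changes against their means.** Gain from the means, with its rounding range, against the printed gain:

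| Outcome | From means | Printed |
|---|---|---|
| Control step | 98 − 92.5 = 5.5 (4.95 to 6.05) | 3.8 |
| VR step | 121 − 96.0 = 25.0 (24.45 to 25.55) | 26.6 |
| Control left reach | 2.9 − 1.4 = 1.5 (1.4 to 1.6) | 0.2 |
| VR left reach | 5.9 − 1.2 = 4.7 (4.6 to 4.8) | 4.9 |
| VR physical QoL | 11.1 − 10.8 = 0.3 (0.2 to 0.4) | 0.1 |

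The step ranges take 98 and 121 as rounded integers.

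**5. The footnote.** Rows marked § as Wilcoxon reproduce as paired t = change/(SD/√n), computed v printed: VR step −26.6/(31.2/√30) = −4.67 v −4.67; VR left reach −3.31 v −3.29; VR physical −1.37 v −1.31; control step −1.46 v −1.47; control left reach −0.77 v −0.79. Control physical cannot be computed from 0.0 ± 0.1. Read as t on 29 df, −3.29 gives p = 0.003 as printed; read as a normal Z it would give 0.001. The unmarked rows carry values such as −140 and −56.5 (p = 0.174), which cannot be t statistics. Because the printed changes fit the printed t statistics, the means in step 4 may be the misprint.

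**The case against.** The strongest reply is that no headline conclusion rests on the misprinted row. The Abstract and the ANCOVA text assign the between-group p-values correctly, Chapter 6 claims no balance or strength effect, and the duplicated label is visible. The strength and balance sentence stands among recommendations and cites no p-value. That limits the damage, but the table still contradicts its own text and the sentence still lacks support.

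Several narrower points stand:
- Table 6 prints no means, so p = 0.418 for the up-and-go is assigned by row order. This is safe: the five rows named in the text fit that order, and every row the text does not name is non-significant.
- Both domains were tested. The defect is that no reported test shows a VR benefit. Chapter 3, Section 4 also plans a comparison of body-angle data, for which no result is reported.
- The formal objective and hypothesis (Chapter 1, Sections 2 and 3) name physical fitness and quality of life. Balance and strength come from Chapter 3.
- The chair-stand gain is significant in the control arm (p = 0.001), with similar mean gains (0.8 v 0.9 in VR). The VR arm may have matched an active comparator.
- The balance statements in Chapter 5, Section 2 and early in Section 4 are more general; the latter speaks of maintaining balance.
- The intervals are rough: they are unadjusted, ignore rounding, and use normal theory.
- PDF extraction cannot be wholly excluded. The same fault in two tables, with Table 4 intact, makes it unlikely.
- This is a reporting error; no choice of method is challenged.

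**Conclusion.** The concern holds and must be fixed. Eight of ten rows in each of Tables 5 and 6 carry the wrong label. The up-and-go is printed with p = 0.002 and partial eta squared 0.151; by row order its values are 0.418 and 0.011. No reported between-group or within-VR test supports the strength and balance parts of the Chapter 5 claim. The flexibility part is supported (right reach p = 0.010, left reach p = 0.002).

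No difference from an active exercise control with 63 analysed is not proof of no effect, so the wording needs correcting and should not be turned into a claim of no benefit. The verdict assumes that Table 6 follows Table 4's row order and that the error df is 58. The second assumption serves only to reproduce the figures.

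**What to change.** 1. Check the source output. If it confirms the shift, relabel rows 3 to 10 of Tables 5 and 6: step, right reach, left reach, up-and-go, then physical, psychological, social and environmental quality of life.
2. Reconcile the five Table 5 means and changes, and rerun a test only if its source data prove wrong. Correct the footnote. Chapter 4, Section 2.2 should then stop calling all four VR results t-tests, since right reach and psychological quality of life carry S values (−140 and −18).
3. In Chapter 5, Section 4, remove or qualify strength and balance as not shown by this study's tests. Qualify the balance statements in Section 2 and early in Section 4 likewise.
4. Subject to the same check:
   - Change chair stands to sit-and-reach in Chapter 5, Sections 1 and 2.
   - Correct the left/right order there and in Chapter 4, Section 2.2 (relabelled Table 5 gives right p < 0.001, left p = 0.003).
   - Reconcile the physical-domain sentence in Chapter 4, Section 3 with Table 7.
5. After steps 1 and 2, replace the broad fitness wording in the Abstract conclusion and Chapter 6 with the named outcomes that remain significant. State that no between-group difference was shown for up-and-go or chair stand. If environmental quality of life stays, print its means beside it (10.6 to 10.6 v 10.3 to 10.3).
6. In Chapter 4, Section 2.3 and Chapter 5, Section 2, do not present the non-significant rows (partial eta squared 0.011 to 0.024) as moderate to substantial intervention effects.

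The cost is one check against the output, then table and text edits. No new data are needed.
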